10.5.4. Efficacy Analyses

In all cases, analyses defined in the SAP take precedence over descriptions in the Protocol.

To address the secondary study objective of assessing evidence of efficacy, the efficacy endpoints of primary interest include the proportion of subjects achieving SRI-4 response at Day 169 and the proportion of subjects achieving BILAG-based Composite Lupus Assessment (BICLA) response at Day 169.

All efficacy measures will be summarized and analyzed for the mITT population.

For categorical endpoints, the number and proportion of subjects in each at each visit will be presented by treatment group. Proportions will be compared using a Cochran-Mantel-Haenszel test adjusted for randomization stratification factors. An estimate of the difference in proportions and corresponding 95% confidence interval will be presented. P-values may be presented for the efficacy endpoints of primary interest.

For continuous endpoints, the mean, standard deviation, median, minimum, and maximum at each visit. For continuous endpoints with multiple post-Baseline visits, the treatment effect will be assessed through Mixed-effect Model Repeated Measures (MMRM) based on observed data.

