4.3. Methods of Assigning Subjects to Treatment

A centralized interactive web-based response system will be used to randomly assign subjects to receive either ALPN-101 or placebo in a 1:1 ratio. Randomization will be stratified by geographic region and by use of concomitant oral immunosuppressive therapy at enrollment. Levels of each stratification factor, which result in 6 unique strata, are defined as follows:

- 1. Background immunosuppressive therapy use:
 - Present: Concomitant use of at least one of the permitted immunosuppressants (e.g., methotrexate, leflunomide, azathioprine, 6-mercaptopurine, mycophenolate mofetil, mycophenolic acid) and/or corticosteroids at doses >5 mg prednisone or equivalent daily with or without hydroxychloroquine/hydroxychloroquine-like drugs;

^{*}Assuming a 2-sided significance level of 0.05 using SAS version 9.4

• Absent: No use of permitted immunosuppressants and/or corticosteroids at doses >5 mg prednisone or equivalent daily, with or without use of lower doses of corticosteroids and/or hydroxychloroquine/hydroxychloroquine-like drugs.

2. Geographic region:

- Region 1: North America or Western Europe
- Region 2: Eastern Europe
- Region 3: Asia

Subjects, investigators, site staff, and individuals with direct contact with site staff (e.g., clinical research associates, project management, medical monitors, and data management) will remain blinded to treatment assignment until after final database lock. Select study team members may be unblinded to treatment assignment. A list of all individuals unblinded to treatment assignment prior to final database lock will be maintained.

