7.4. Analysis of Efficacy Endpoints

7.4.1. General Considerations

Unless otherwise stated, all efficacy analyses will be conducted on the mITT population according to the randomized treatment. For efficacy endpoints, point estimates of treatment differences and 95% confidence intervals (CI) will be provided. Two-sided p-values will also be provided for efficacy endpoints, as applicable. Where possible, study outcomes will be presented graphically also. Due to small sample sizes of subjects randomized to the Asia geographic region, this region will be pooled with the Eastern Europe region in the statistical analysis models.

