7.5. Analysis of Primary Efficacy Endpoints

7.5.1. Main Analysis

Response rates for subjects in the ALPN-101 group and in the placebo group will be calculated and the corresponding 95% CI will be reported for each treatment group. These response endpoints will be analyzed through Day 169 for subjects who complete treatment and through

the last assessment recorded ≤28 days after treatment discontinuation date for subjects who discontinue treatment early.

For the main analyses of SRI-4 response rate and BICLA response rate, non-responder imputation will be used for IE and missing data as described in Section 7.4.2.

Response rates will be compared using Cochran-Mantel-Haenszel (CMH) test statistic stratified by the factors used at randomization. Estimated treatment effect will be reported as the difference between the response rate in the ALPN-101 treatment group and the response rate in the placebo group. Corresponding 95% CI for the difference in proportions and the two-sided p-value for the difference will be reported.

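### The primary efficacy test is stratified, but as worded the reported difference in response rates and its 95% CI are not tied to the randomisation strata

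*SAP*

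**What the plan says.** SAP 7.5.1 (Main Analysis) covers both primary efficacy endpoints, SRI-4 and BICLA at Day 169.

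- **Arm rates:** "Response rates for subjects in the ALPN-101 group and in the placebo group will be calculated", with a 95% CI for each group. No stratum weighting is mentioned.
- **Test:** "Response rates will be compared using Cochran-Mantel-Haenszel (CMH) test statistic stratified by the factors used at randomization".
- **Effect:** "Estimated treatment effect will be reported as the difference between the response rate in the ALPN-101 treatment group" and the placebo rate.
- **Interval:** "Corresponding 95% CI for the difference in proportions and the two-sided p-value for the difference will be reported". No method is named.

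Protocol 10.5.4 has the same shape. The test is adjusted ("Proportions will be compared using a Cochran-Mantel-Haenszel test adjusted for randomization stratification factors"), and then "An estimate of the difference in proportions and corresponding 95% confidence interval will be presented", with nothing on adjustment. SAP 7.6.1 carries the 7.5.1 approach over to the other categorical endpoints. SAP Table 2 gives the summary measure as a difference in proportions and does not mention strata. The CMH code in SAP Section 13 requests the test and no risk difference.

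Elsewhere the SAP does adjust its estimates. The MMRM and analysis of variance in 7.6.2 and the Cox model in 7.6.3 all include the stratification factors.

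On the strata themselves, SAP 4.3 defines two therapy levels and three regions, "which result in 6 unique strata". SAP 7.4.1 says of Asia that "this region will be pooled with the Eastern Europe region in the statistical analysis models". Section 7.5.1 refers only to the randomisation factors.

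**The concern.** Stratified randomisation balances the arms within strata. If response differs between strata, that balance reduces the sampling variability of the treatment difference. The CMH test takes credit for this. An interval built from two simple arm proportions does not, because its standard error still contains the between-stratum spread. The interval then overstates the uncertainty, and a table can show a p-value below 0.05 beside a CI that includes zero, or the reverse.

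Enrolment stopped at 76 of the planned 130, and neither document sets a formal efficacy success rule. Readers will therefore judge efficacy largely from the difference and its CI, and for the two leading efficacy endpoints neither the estimator nor the interval method is fixed in the text.

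**Working it through.** **1. The plan's own figure.** Inputs from SAP 4.2 and Protocol 10.2: 65 per arm, two-sided 0.05 chi-square, 40% vs 65% (SRI-4) and 20% vs 45% (BICLA). Power = Φ[(d − 1.96·SE0)/SE1], where SE0 uses the pooled rate and SE1 the separate rates.

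- SRI-4: SE0 = √(2×0.525×0.475/65) = 0.0876; SE1 = √((0.40×0.60 + 0.65×0.35)/65) = 0.0848; (0.25 − 1.96×0.0876)/0.0848 = 0.92; power 82.2%.
- BICLA: SE0 = 0.0822; SE1 = 0.0792; ratio 1.12; power 86.9%.

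The plan states 82% and 87%, so both reproduce. They are unstratified and do not change under this point.

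**2. Number of strata.** Randomised: 2×3 = 6. After pooling Asia with Eastern Europe: 2×2 = 4, or 76/4 = 19 subjects per stratum on average.

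**3. Can the CI and p-value conflict?** A constructed example, chosen to show that it can happen and not as a typical result, with 38 per arm:

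| Stratum | ALPN-101 | Placebo | Difference d | Weight w = n1·n0/n |
|---|---|---|---|---|
| 1 | 2/13 | 2/14 | 0.011 | 6.741 |
| 2 | 2/6 | 0/5 | 0.333 | 2.727 |
| 3 | 13/13 | 9/13 | 0.308 | 6.500 |
| 4 | 6/6 | 4/6 | 0.333 | 3.000 |
| Total | 23/38 | 15/38 | | 18.968 |

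- CMH: expected ALPN-101 responders 1.926 + 1.091 + 11 + 5 = 19.017; variance 0.883 + 0.446 + 0.880 + 0.455 = 2.664; χ² = (23 − 19.017)²/2.664 = 5.96; p = 0.015.
- Simple difference: 0.605 − 0.395 = 21.1%; Wald SE = √(2×0.605×0.395/38) = 0.112; 95% CI −0.9% to 43.0%, which includes zero.
- Mantel-Haenszel: Σw·d/Σw = (0.074 + 0.909 + 2.000 + 1.000)/18.968 = 21.0%. Sato variance = (d_MH·ΣP + ΣQ)/(Σw)², with P = [n1²x0 − n0²x1 + n1n0(n0 − n1)/2]/n² and Q = [x1(n0 − x0) + x0(n1 − x1)]/(2n). Here ΣP = −1.986 and ΣQ = 2.806, so SE = √(0.210×(−1.986) + 2.806)/18.968 = 0.0815; 95% CI 5.0% to 37.0%, which excludes zero.

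The reverse also occurs. With the same stratum sizes and responders 3, 3, 8, 3 vs 4, 2, 2, 1 (17/38 vs 9/38), CMH p = 0.063, the simple CI is 0.3% to 41.9%, and the Mantel-Haenszel CI is −0.7% to 41.8%.

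**4. How often, and how much?** Simulation at N=76: 40,000 trials per scenario, four strata, placebo rates 40% and 20%, effect 0 or 25 points, Wald CI for the simple difference. The documents give no stratum response rates, so these inputs are assumptions: stratum shares 35/15/35/15%; blocks of 4; log-odds offsets none, moderate (0, 0.5, 0.7, 1.2) or strong (0, 1, 1.5, 2.5). At a 40% placebo rate, strong means stratum rates of about 18%, 37%, 49% and 73% (0.35×18 + 0.15×37 + 0.35×49 + 0.15×73 = 40).

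| Quantity | Simple | Mantel-Haenszel |
|---|---|---|
| Conflict with CMH p, 25-point effect | 0.9–5.4% of trials | 1.4–2.5% |
| Conflict with CMH p, no effect | 0.6–1.6% | 0.7–0.9% |
| Mean CI width, largest gap (40% placebo, no effect, strong strata) | 43.5 points | 40.1 points |
| Coverage of the 95% CI | 93.9–96.3% | about 94% |

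The largest narrowing is (43.5 − 40.1)/43.5 = 7.8%. It is about 2% with moderate strata and nil with none. The two point estimates differ by 0.3 to 0.9 points on average and have essentially the same sampling SD. The gain is an interval that reflects the design, not a better point estimate.

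**5. Sensitivity to the layout.** With four near-equal, perfectly balanced strata (20,000 trials, 40% vs 65%) and stratum rates spanning 10, 20 and 30 points, the Mantel-Haenszel CI is only 0.5%, 1% and 3% narrower. It conflicts with the CMH p-value more often: 0.9%, 1.6% and 2.5% of trials, against 0.2%, 0.5% and 1.1% for the simple CI. At a 60-point span the order reverses, 2.3% against 9.0%.

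**The case against.** **The SAP never says the difference is crude or unadjusted.** A reader might infer that the estimate and CI definitely ignore the strata. The documents do not support that. The CI sentence closes a paragraph on a stratified test, 7.6.1 calls the approach stratified CMH, and a stratified risk difference would contradict no sentence. The contents list also shows a 7.5.2.1 on robustness of imputation that is absent from the public text. This stands, and it limits the point to what the wording fixes: the plain reading is the simple difference, and nothing ties the estimate to the strata.

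**A simple difference is not wrong.** This also stands. It validly estimates the difference in proportions in Table 2, with coverage between 93.9% and 96.3%. A reader might infer bias or an invalid interval, but the calculations show neither.

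**The remedy does not guarantee agreement.** This stands too. Part of the conflict comes from Wald versus CMH variance and not from strata. At 40% vs 65% with null or moderate strata, a further run gave 1.2–1.8% conflict for Mantel-Haenszel against 0.6–1.2% for the simple CI.

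**The stakes are limited.** Safety is the primary objective, the sample size was not derived for formal efficacy testing, and there is no multiplicity control. No confirmatory decision turns on this.

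What the objections do not answer is why the SAP adjusts its other modelled estimates for strata and leaves these two endpoints without an adjusted estimator or a named interval.

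**Conclusion.** The point holds in a limited form. The test for SRI-4 and BICLA is stratified. As worded, the estimate is the simple difference between arms, and its interval method is unnamed and not linked to the strata.

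The practical effect is modest and depends on how prognostic therapy and region are, which the documents do not say. Under the main assumed scenarios at N=76, a stratified CI is about 2% (moderate) to 6–8% (strong) narrower, and conflict with the CMH p-value falls from up to about 5% of trials to about 2.5%. With non-prognostic strata nothing is gained. With weak strata, Mantel-Haenszel conflict can be slightly higher. The Sato interval covers at about 94%, a little under nominal, while the simple interval drifts to about 96% when strata are strong.

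A separate but connected ambiguity is firm whatever the assumptions: 7.5.1 points to the randomisation factors (six strata), and 7.4.1 pools to four.

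**What to change.** In SAP 7.5.1, name the reported effect as the Mantel-Haenszel common risk difference, with a stratified 95% CI (for example Sato variance or stratified Miettinen-Nurminen), computed over the same strata as the CMH test. State that these are the four strata after Asia is pooled with Eastern Europe (7.4.1), not the six randomised strata. Keep the simple response rates per arm, with their CIs, as description. Apply the same wording in 7.6.1, and align the CMH code in Section 13 with the stated strata.

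The text should not promise that the CI and p-value will always agree.

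The cost is about one sentence in each section and a standard software option. No data collection, sample size or power figure changes. The choice should be documented before treatment assignments are unblinded for analysis.

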7.6. Analysis of Secondary Efficacy Endpoints

Unless otherwise stated, the mITT population will be the basis for analyses of all efficacy endpoints. These data will be analyzed through Week 24 (Day 169) for subjects who complete treatment and through the last assessment recorded \leq 28 days after treatment discontinuation for subjects who discontinue treatment early.

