- Significant non-compliance with study procedures to a degree that would put the subject at risk for continued participation in the trial as determined by the Investigator or the Medical Monitor.

• Development of active neuropsychiatric SLE (excluding lupus headache) sufficiently severe to interfere with ability of the subject to provide ongoing informed consent.

• Investigator decision: Investigator believes it is in the best interest of the subject to discontinue treatment with study drug.

Subjects who prematurely discontinue treatment with study drug should have all procedures outlined in the EoT visit, as well as an unscheduled ECG, performed as soon as possible, and not later than the next scheduled visit.

To minimize missing data for efficacy and safety assessments, subjects who prematurely discontinue treatment, and who do not withdraw consent, should otherwise continue with their regular study visit schedule without receiving study drug. In subjects who are unable to continue their regularly scheduled visits, a follow-up phone call should occur approximately 8 weeks (corresponding to 5X half-life) after the last dose of study drug to determine the status of any ongoing AEs/SAEs or the occurrence of any new AEs/SAEs.

Discontinuation from the Study (Early Termination)

In addition to the criteria for discontinuing study drug summarized above, individual subjects may be discontinued from the study prematurely (i.e., prior to Day 197) for any of the following reasons:

- Subject decision / withdrawal of consent; subjects can request to be discontinued from participation in the study at any time for any reason
- Investigator decision: Investigator believes it is in the best interest of the subject to be withdrawn from the study

For subjects who withdraw from the study prematurely (i.e., prior to Day 197), the End of Study (EoS) evaluations should be completed if possible, preferably within 2 weeks of study drug discontinuation. In addition, a follow-up phone call should occur approximately 8 weeks (corresponding to 5X half-life) after the last dose of study drug to determine the status of any ongoing AEs/SAEs or the occurrence of any new AEs/SAEs.

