If during the Treatment period (Day 1 to 169) the SOC medications used at Baseline, together with the permitted bursts and taper of corticosteroids, are considered to not be adequate for the treatment of increased disease activity, a subject may receive medications deemed necessary by the Investigator or treating physician. In that case, all of the following should be done:

- Blinded study drug will be discontinued
- The subject should remain in the study for assessment of outcomes, including safety
- The Investigator should consult the Medical Monitor AND the updated IB to discuss any additional safety assessments to be performed in addition to those included in the protocol

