3.1.2. Secondary Efficacy Endpoints

Secondary efficacy endpoints are provided below:

- Annualized flare rate by British Isles Lupus Assessment Group (BILAG)-2004 flare index through Day 169 all flares
- Time-to-first flare by BILAG-2004 flare index
- Achievement of Lupus Low Disease Activity State (LLDAS) at Day 169
- Change from baseline in Systemic Lupus Erythematosus Disease Activity Index 2000 (SLEDAI-2K) total score at Day 169
- Cumulative prednisone-equivalent dose use (total area under the curve of daily prednisone-equivalent dose) through Day 169
- Achievement of ≥50% reduction in Cutaneous Lupus Erythematosus Disease Area and Severity Index (CLASI) activity score at Day 169 in the subgroup of subjects with baseline CLASI activity score ≥8

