7.4.2. Handling of Missing Data and Intercurrent Events (IE)

Intercurrent events in this study include the following:

- IE1: Premature discontinuation of study treatment
- IE2: Restricted/rescue medication use (criteria for restricted/rescue medication use is provided in Section 6.21)

The strategies to be used in the handling of intercurrent events and missing data for efficacy endpoints, when applicable, are provided below:

- Binary endpoints (primary and secondary efficacy endpoints):
 - IE1 and IE2: subject is considered a non-responder (composite strategy)
 - Missing data for Day 169: subject is considered a non-responder
- Continuous endpoints measured through time (SLEDAI-2K total score):
 - IE1 and IE2: data after IE1 and IE2 occurs will not be included in the analysis (hypothetical strategy)
 - Missing data caused by applying the intercurrent event handling described above and other missing data will be handled by the mixed effects models for repeated measures (MMRM) analysis
- Other efficacy endpoints:
 - Treatment policy strategy will be applied and all observed data during the treatment period will be used regardless of IE1 or IE2
 - Missing data for Day 169 for binary endpoints: subject is considered a non-responder for applicable endpoints

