7.7. Estimands for the Primary and Secondary Endpoints

Estimand definitions for the primary and secondary efficacy endpoints are provided below:

Table 2: Estimand Attributes Corresponding to the Primary and Secondary Efficacy Endpoints

	Attributes of the Estimand						
Estimand	Treatment	Endpoint	Population	Handling of Intercurrent Events	Statistical Summary		
Primary	ALPN-101 vs. Placebo	Achievement of SRI-4 response at Day 169	Subjects with moderate to severe SLE	IE1 and IE2: subject is considered a non-responder (composite strategy) Missing data: subject is considered a non-responder	Difference in the proportion of subjects achieving SRI- 4 response		
Primary	ALPN-101 vs. Placebo	Achievement of BICLA response at Day 169	Subjects with moderate to severe SLE	IE1 and IE2: subject is considered a non-responder (composite strategy) Missing data: subject is considered a non-responder	Difference in the proportion of subjects achieving BICLA response		
Secondary	ALPN-101 vs. Placebo	Annualized flare rate by BILAG- 2004 flare index through Day 169 for all flares	Subjects with moderate to severe SLE	All observed data used (treatment policy strategy)	Difference in the LS means for annualized flare rate by BILAG-2004 flare index for all flares		
Secondary	ALPN-101 vs. Placebo	Time-to-first flare by BILAG- 2004 flare index	Subjects with moderate to severe SLE	All observed data used (treatment policy strategy)	Hazard ratio for time-to- first flare by BILAG-2004 flare index		
Secondary	ALPN-101 vs. Placebo	Achievement of LLDAS response at Day 169	Subjects with moderate to severe SLE	IE1 and IE2: subject is considered a non-responder (composite strategy) Missing data: subject is considered a non-responder	Difference in the proportion of subjects achieving LLDAS response		

	Attributes of the Estimand						
Estimand	Treatment	Endpoint	Population	Handling of Intercurrent Events	Statistical Summary		
Secondary	ALPN-101 vs. Placebo	Change from baseline in SLEDAI-2K total score at Day 169	Subjects with moderate to severe SLE	All observed data used (hypothetical strategy)	Difference in the LS means for change from baseline in SLEDAI- 2K total score		
Secondary	ALPN-101 vs. Placebo	Cumulative prednisone- equivalent dose use through Day 169	Subjects with moderate to severe SLE	All observed data used (treatment policy strategy)	Difference in the LS means for cumulative prednisone- equivalent dose use		

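### SAP 7.6 cuts early stoppers' data 28 days after stopping, against the treatment-policy strategy the SAP sets for three secondary endpoints

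*SAP*

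**What the plan says.** **The cut-off.** SAP 7.6 covers all secondary efficacy endpoints. Completers are analysed through Day 169. Early stoppers are analysed through the last assessment no later than "28 days after treatment discontinuation for subjects who discontinue treatment early". No endpoint is exempted.

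**The strategy.** SAP 7.4.2 lists premature discontinuation of study treatment as intercurrent event IE1 and restricted or rescue medication as IE2. For efficacy endpoints other than the binary ones and SLEDAI-2K over time, it says: "Treatment policy strategy will be applied and all observed data during the treatment period will be used regardless of IE1 or IE2". SAP 7.7, Table 2, then names annualized flare rate, time to first flare and cumulative prednisone-equivalent dose, each with the entry "All observed data used (treatment policy strategy".

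**The time horizon.** SAP 3.1.2 defines the flare rate by the BILAG-2004 "flare index through Day 169 all flares", and the steroid endpoint as "Cumulative prednisone-equivalent dose use (total area under the curve of daily prednisone-equivalent dose) through Day 169". Protocol 8.2.2.3 gives the period in passing: "during the Treatment period (Day 1 to 169".

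**Follow-up after stopping.** Protocol 4.3.2 says early stoppers who do not withdraw consent "should otherwise continue with their regular study visit schedule without receiving study drug". Protocol 6.6.1 and SAP 4.1 agree. For subjects taken off drug because permitted treatment was inadequate, Protocol 8.2.2.3 adds: "The subject should remain in the study for assessment of outcomes, including safety".

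**The concern.** Treatment policy means that outcomes after stopping drug count. A 28-day limit removes most of that off-drug period for anyone who stops in the first half of the study. The two instructions therefore target different quantities, and an analyst following 7.6 would not estimate what Table 2 declares.

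The removed period is unlikely to resemble the period kept. Protocol 6.6.1 lifts the concomitant medication restrictions once study drug is stopped, and Protocol 8.2.2.3 has study drug discontinued when permitted treatment is not enough for increased disease activity. Steroid use and flares after stopping can therefore differ from those before.

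Cumulative prednisone is the most exposed endpoint. It is an unscaled total, and the analysis of variance in SAP 7.6.2 has no term for length of follow-up, so truncation lowers a stopper's value mechanically.

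Two competent programmers could produce different results for three of six secondary endpoints. Choosing between them after unblinding would be a data-dependent decision.

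**Working it through.** The plan gives no figure on this point to reproduce. The check is a comparison of text, followed by day arithmetic.

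**1. Do the rules cover the same endpoints?** SAP 7.4.2 has three groups: binary endpoints (composite strategy), SLEDAI-2K total score over time (hypothetical) and the rest (treatment policy). Flare rate, time to first flare and cumulative prednisone fall in the third group by elimination, and Table 2 confirms this by name. SAP 7.6 also covers them.

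**2. Could treatment period mean the subject's own time on drug?** If the period ended at discontinuation, the clause about using data regardless of IE1 would be empty. Two of the endpoints run through Day 169, and Protocol 8.2.2.3 gives Day 1 to 169. Even time on drug would not equal stop day plus 28.

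**3. How much data does the cut drop?** Inputs: BILAG visits after baseline through Day 169 fall on Days 29, 57, 85, 113, 141 and 169 (Protocol Table 1). Cut-off day = min(169, stop day + 28). Days lost = 169 − cut-off day. Nominal visit days are used.

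| Stop day | Cut-off day | BILAG visits dropped (of 6) | Days dropped (of 169) |
|---|---|---|---|
| 29 | 57 | 4 | 112 (66%) |
| 57 | 85 | 3 | 84 (50%) |
| 85 | 113 | 2 | 56 (33%) |
| 113 | 141 | 1 | 28 (17%) |
| 141 | 169 | 0 | 0 |

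**4. Effect on one subject who stops at Day 57 and keeps attending.**
- One flare, at Day 113: annualized rate 365.25/169 = 2.16 with all data, 0 under the cut. In time to first flare, the event becomes a censored time at Day 85.
- One flare, by Day 57: 365.25/169 = 2.16 with all data, 365.25/85 = 4.30 under the cut.
- Prednisone at an assumed constant 10 mg/day: 10 × 169 = 1690 mg with all data, 10 × 85 = 850 mg under the cut.

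**5. Effect on the steroid contrast between arms (assumed values).** Take identical use of 10 mg/day in both arms, 25% of ALPN-101 and 10% of placebo subjects stopping on the same day, and a last retained assessment exactly 28 days after stopping. The spurious difference is (0.25 − 0.10) × 10 × days lost:
- Day 57: 0.15 × 10 × 84 = 126 mg lower on ALPN-101
- Day 29: 0.15 × 10 × 112 = 168 mg lower
- Day 113: 0.15 × 10 × 28 = 42 mg lower

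It is zero with equal stopping and reverses sign if the rates are swapped.

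**6. Related wording on censoring.** SAP 6.9 censors subjects without a flare at the EOT date. SAP 7.6.3 censors them at the last available BILAG. The EOT date is not defined for early stoppers: SAP section 12 labels the visit Day 169/EOT, while SAP 4.1 has early stoppers complete the EOT procedures when they stop. SAP 6.7 and 7.6.3 differ in the same way for time to first BICLA response.

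The effect was calculated from the large-sample Cox score on expected counts. Assumptions: the same flare hazard in both arms (true hazard ratio 1.0), flares seen at the next BILAG visit, stop day equally likely at Day 29, 57, 85 or 113, and stopping of 25% versus 10%.
- EOT read as the stop visit while flares to Day 169 still count: hazard ratio 1.083, 1.062 and 1.046 at 1, 2 and 3 flares per year. With the stopping rates swapped: 0.924, 0.941 and 0.956.
- EOT read as Day 169, or the 28-day cut with last-BILAG censoring: 1.000.

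**7. Related wording on exposure time.** SAP 6.10 counts flares in the treatment period but runs exposure to the last BILAG, without repeating the Day 169 limit. BILAG is also scheduled at Day 197 (Protocol 6.5). Read literally, a completer with one flare has a rate of 365.25/197 = 1.85 instead of 2.16.

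**8. The other endpoints.** SRI-4, BICLA, LLDAS and the CLASI 50% response are not materially affected, because early stoppers are already non-responders. For SLEDAI-2K, 7.4.2 excludes all data after IE1 or IE2. The 28-day limit is looser, so 7.6 adds no conflict there. The Table 2 cell, however, says all observed data are used under a hypothetical strategy, which contradicts 7.4.2.

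**The case against.** The best counter-reading is that the specific governs the general. SAP 7.4.2 is the section on intercurrent events, Table 2 applies it endpoint by endpoint, and 7.6.3 gives time to first flare its own censoring rule with no 28-day limit. On that view the sentence in 7.6 is carried over from 7.5.1, where it does little harm. A sensible analyst might settle it this way, but the SAP does not say so. The qualifier opening 7.6 attaches to the sentence on the mITT population, not to the cut-off.

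A second reading uses SAP 4.1, where the treatment period is up to 24 weeks, and SAP 7.2, which sums steroid exposure while on study treatment. Both leave room for a shorter period per subject. Step 2 of the working shows why this does not reconcile the rules.

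On size, much of the objection stands:
- The flare rate is divided by exposure. With a constant flare probability per visit, the cut moves it by only about 1% (2/57 = 0.0351, 3/85 = 0.0353, 6/169 = 0.0355 visits per day).
- The hazard ratio shift arises only on one combined reading of EOT, not from the 28-day cut.
- The steroid figures rest on assumed rates and dose.
- Visit windows of ±3 days mean that a Day 141 stopper seen on Days 170 to 172 would also lose that visit, so the zero in the table is nominal.
- These are secondary endpoints in a study whose primary objective is safety, with no multiplicity control and enrollment stopped at 76, about 38 per arm.

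Relabelling the strategy as while-on-treatment plus 28 days would also remove the contradiction. It would, however, replace the strategy the SAP names and require rewriting 7.4.2, Table 2 and the Day 169 horizons.

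**Conclusion.** The concern holds. SAP 7.6 as written contradicts SAP 7.4.2 and Table 2 for three of six secondary endpoints, and following it would not estimate the stated estimand. This is an error in the text rather than missing detail.

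The loss of data for an individual follows from the documents on nominal visit days: up to four of six BILAG visits and 66% of the steroid period for a Day 29 stopper, falling to nothing for a Day 141 stopper. The effect on the treatment contrast cannot be determined from the documents, which give neither discontinuation rates nor steroid doses. Cumulative prednisone is the endpoint most open to bias. For flare rate and time to first flare, the cut alone does little if flare risk is unchanged after stopping; distortion there needs off-drug behaviour to differ. The point should be fixed, but it does not touch the safety objective or materially affect the SRI-4 and BICLA analyses.

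**What to change.** Amend the SAP before unblinding:

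1. **7.6:** exempt annualized flare rate, time to first flare and cumulative prednisone-equivalent dose from the 28-day sentence. State that all observed data through the Day 169 analysis visit are used (for prednisone, doses through Day 169).
2. **6.9 and 7.6.3:** use one censoring rule, the last non-missing BILAG up to and including the Day 169 analysis visit. Align 6.7 in the same way, with the last non-missing response assessment.
3. **6.10:** end both the flare count and the exposure time at the last BILAG up to and including the Day 169 analysis visit.
4. **Table 2, SLEDAI-2K row:** state that data after IE1 or IE2 are excluded (hypothetical strategy) and that the analysis is by MMRM.

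The cost is SAP wording only. The protocol already asks early stoppers to keep attending visits, so no new data collection is needed, and SAP section 8 already provides for an amendment.
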